### 1.8. TREATMENT OPTIONS

The range of available treatment options for NMSC includes surgery, cryotherapy, curettage and electrodesiccation, radiation therapy including superficial radiation therapy, photodynamic therapy, various forms of brachytherapy, and chemotherapeutic agents. Treatment decisions may be based on tumor type, anatomical location, patient age, tumor stage and classification, physician preference, and treatment setting. The choice of treatment becomes more complex among the elderly due to frailty, limited life-expectancy, and comorbidities. Anatomical location also becomes an important factor as NMSC lesions commonly occur on the ears, eyes and nose where treatment may have significant cosmetic consequences.

This study will focus on evaluation of outcomes of Superficial X-ray Therapy (SRT), a non-surgical option for patients with primary non-aggressive BCC and SCC and for patients who decline surgery or are poor surgical candidates.

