### **5.4.1. Inclusion Criteria**

1. Male or female.
2. Treatment with SRT-100™.
3. Treatment date of December 31, 2015 or earlier.
4. Non-Melanoma Skin Cancer (NMSC) pathological diagnosis of confirmed squamous cell carcinoma (SCC) or basal cell carcinoma (BCC).

5. Histopathological Grade: G1 (well differentiated); G2 (moderately differentiated) or Gx (not assessed).
6. One lesion is treated, or more than one lesion is treated with a minimum of a 5 mm gap between the edges of the lesion margins.
7. Required retrospective data is existing and sufficient.

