#### **5.4.2. Exclusion Criteria**

1. Lesions of etiology other than non-melanoma skin cancer (NMSC).

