#### **A. Patient Information and Demographics:**

1. Gender
2. Age at treatment start

3. Ethnicity
4. Significant comorbidities

B. Lesion Diagnostic Variables and Characteristics:

1. Pathology diagnosis
2. Diagnosis subtype/variant
3. Other pathology
4. Recurrent lesion (yes/no)
5. Previous treatment if recurrent
6. Lesion location (no restrictions): scalp, mastoid, forehead, cheek, nose, ear, chin, lips, neck, upper arm, lower arm, hand, upper leg, lower leg, foot.

C. Lesion Size and Margins:

1. Lesion size
2. Treatment margin
3. Lead cutout size
4. Applicator size

D. Treatment Dosage and Schedule:

1. Treatment dose
2. Number of treatments
3. Number of treatments per week
4. Treatment span(days)

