**F. Follow-Up:**

1. Time in months since the most recent follow-up since end of treatment
2. Recurrence: Yes/No
3. Recurrence treatment and outcome (as applicable)
4. Follow-up notes (as applicable)

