**7. REGISTRY ADMINISTRATION**

Existing patient medical records will only be reviewed by study site staff who already have access to the files and who have been trained to the study protocol. Once a qualifying patient medical record is identified, the study site staff member will extract only the required data elements and enter them directly into an Excel database provided by the study Sponsor.

There will be no identifying information entered into the database that could potentially connect an individual data record to an individual patient. Unique de-identified codes will be used for each patient data set entered into the database.

The collected retrospective data will only be used for the purposes of evaluating the primary and secondary objectives of this study.

The parties who will have access to the retrospective data and database will be study site investigators and designated study site staff, the study Sponsor and the study biostatistician.

Access to the database will not be given to outside parties at any time during the data collation and analysis process or in the future for any reason.

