#### **10.1.1. Cure Rate**

Cure rate will be calculated as the percentage of lesions that attained complete cure following treatment completion, reported as the overall success rate.

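### SRT-100 need not be a lesion's only treatment, and other treatment is only partly recorded, so some cures could be wrongly attributed to it

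*Combined protocol and SAP*

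**What the plan says.** **Eligibility.** The treatment criterion in Section 5.4.1 (item 2) is "Treatment with SRT-100™". The only exclusion in Section 5.4.2 is "Lesions of etiology other than non-melanoma skin cancer (NMSC". Neither makes SRT the sole treatment of the lesion.

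**Data elements (Section 6.3).** Block B asks for "Recurrent lesion (yes/no" and then for "Previous treatment if recurrent". Block D holds radiation parameters only. Block E has a yes/no cure field and optional notes. Block F has a yes/no recurrence field, "Recurrence treatment and outcome (as applicable", and optional follow-up notes.

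**Analysis.** Section 10.1.1 defines the cure rate as the "percentage of lesions that attained complete cure following treatment completion, reported as the overall success rate". Section 10.1.2 plans Kaplan-Meier estimates and a Cox model on sex, age, lesion type and size, total dose and TDF. Neither recurrent status nor other treatment is in the model.

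**Traceability.** Under Section 7, site staff "extract only the required data elements". Under Section 7.2.1, the sheets linking codes to charts are destroyed once the data have been entered and checked.

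**The concern.** The primary objective is the long-term efficacy of SRT-100, and there is no control arm. The cure rate and recurrence curve speak for SRT-100 only if the lesions in them were controlled by it. Section 1.8 lists several other modalities used for these cancers, among them "surgery, cryotherapy, curettage and electrodesiccation, radiation therapy including superficial radiation therapy, photodynamic therapy". A primary lesion that had one of these before or during its SRT course meets the written criteria, and no coded entry would show it.

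Such lesions would be pooled with lesions treated by SRT alone. They could not be reliably excluded, stratified or adjusted for, and after destruction of the link sheets the database could not be checked against the charts. The secondary analyses of outcome by dose and fractionation would rest on the same mixed set.

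**Working it through.** **1. Which other treatment has a coded field (Section 6.3, A to F)**

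| Other treatment of the lesion | Primary lesion | Recurrent lesion |
|---|---|---|
| Before SRT | none | B.5 |
| During SRT | none | none |
| After SRT, for a recurrence | F.2, F.3 | F.2, F.3 |
| After SRT, not called recurrence treatment | none | none |

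The notes in E.4 and F.4 could hold any of these, but no instruction requires it. Section 1.6 names evidence of prior surgery or treatment as part of clinical assessment, so some charts may contain the information.

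**2. Effect on recurrence (illustration)**

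The documents give no share of lesions with other treatment and no outcome for them, so there is no planned figure to reproduce. The one anchor is the 5-year cumulative recurrence of 5.0% in the earlier study abstracted in Section 3, used here as if it were the observed rate R. Assumed inputs are f, the share of lesions with other treatment, and q, their recurrence rate. Observed recurrence is R = (1 − f)·r + f·q, so recurrence after SRT alone is r = (R − f·q)/(1 − f).

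Example: f = 20%, q = 2% gives (5.0 − 0.20 × 2)/0.80 = 4.6/0.80 = 5.75%.

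| f | q = 0% | q = 2% | q = 5% | q = 10% |
|---|---|---|---|---|
| 5% | 5.26% | 5.16% | 5.00% | 4.74% |
| 10% | 5.56% | 5.33% | 5.00% | 4.44% |
| 20% | 6.25% | 5.75% | 5.00% | 3.75% |
| 30% | 7.14% | 6.29% | 5.00% | 2.86% |

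The difference is r − R = f·(R − q)/(1 − f), so its sign depends only on whether q lies below or above R. Pooling flatters SRT if lesions with other treatment recur less often, does nothing if they recur equally often, and understates SRT if they recur more often.

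**3. Effect on the cure rate (illustration)**

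Assume 90% cure with SRT alone and 98% with other treatment added. The reported rate is (1 − f) × 90% + f × 98%:

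- f = 10%: 81.0 + 9.8 = 90.8%
- f = 20%: 72.0 + 19.6 = 91.6%
- f = 30%: 63.0 + 29.4 = 92.4%

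The true 10% failure rate would read as 9.2%, 8.4% or 7.6%, a relative understatement of 8%, 16% or 24%. The direction follows wholly from having assumed 98% against 90%.

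**4. Residual tumour treated after SRT (illustration)**

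Let u be the share not cured by SRT and c the part of that share treated by other means and entered as cured. Reported cure is 1 − u + u·c.

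- u = 5%: 95.0% at c = 0, 97.5% at c = 0.5, 100% at c = 1
- u = 10%: 90%, 95% and 100% for the same values of c

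Values of c above 0 require a reading of the cure field that Section 10.1.1 does not favour.

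**The case against.** **Treatment after SRT is partly covered.** A reader might infer that salvage after SRT is hidden altogether. The documents do not support that. A treated recurrence is marked in F.2, described in F.3, and can count as an event in the Kaplan-Meier analysis. This stands. The remaining gap after SRT is treatment of a persisting lesion, or added treatment, that nobody calls a recurrence.

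**A persisting lesion would normally be coded as not cured.** Section 10.1.1 ties cure to the end of treatment, and the cure field stands between the SRT parameters and the follow-up block. This largely stands, so step 4 shows a possible coding error rather than an expected one. Still, no assessment time is given and no rule says how such a lesion is coded.

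**Combined treatment may be uncommon.** Section 1.8 presents SRT as a non-surgical option for primary, non-aggressive lesions and for patients who decline surgery or are poor candidates for it. That may make excision plus SRT less typical, but it is not an eligibility rule and says little about topical treatment, curettage or cryotherapy.

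**The bias could go either way.** This stands in full. A lesion excised with residual tumour before SRT might do worse than average.

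**Limiting the main result to lesions without other treatment would change the population.** This also stands. The registry admits recurrent lesions and asks for their previous treatment, so such a restriction would remove many of them. The SRT-alone analysis should therefore be added beside the all-lesion one.

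**Conclusion.** The gap is real and can be read directly from the text. No criterion requires SRT-100 to be the only treatment. No coded field covers prior treatment of a primary lesion, treatment alongside SRT for any lesion, or treatment after SRT that is not called recurrence treatment. Some cures could be wrongly attributed to SRT-100, and the lesions concerned could not be identified once the link sheets are gone.

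Two stronger conclusions are tempting and should not be drawn. One is that cures produced by other treatments are in fact being credited to SRT-100; the documents do not show that any lesion had combined treatment. The other is that the error favours the sponsor; that follows only if lesions with other treatment do better.

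With an observed recurrence of 5.0%, a share of 5% to 30% and recurrence of 0% to 10% among those lesions, SRT-alone recurrence ranges from 2.86% to 7.14%. All inputs except the 5.0% are assumptions, and the 5.0% comes from a different study. The actual size and direction cannot be determined from the documents. The change is worth making because it is cheap while charts are open and cannot be made afterwards.

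**What to change.** 1. **Section 6.3 B.5.** Replace it with an element completed for every lesion: *Other treatment to this lesion (diagnostic biopsy excepted): none / before SRT / during SRT / after SRT / not documented, with type.* For a recurrent lesion, let the entry show whether treatment before SRT belonged to the earlier episode or the current one. State that *not documented* does not make a record ineligible under inclusion item 7, which requires sufficient data.
2. **Section 10.1.1.** State that a lesion needing further treatment for residual tumour after SRT counts as not cured.
3. **Sections 10.1.1 and 10.1.2.** Keep the all-lesion analysis. Add a pre-specified cure rate and Kaplan-Meier curve for lesions with no other definitive treatment in the current episode before or during SRT. Keep previously treated recurrent lesions and show them as their own stratum. Show *not documented* lesions as a separate row rather than assuming SRT alone.

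The cost is one extra extraction column, filled from charts that are already open, and a short protocol change. Some entries will be *not documented*, and the SRT-alone set will be smaller, with a rate that may differ in either direction. Charts already extracted need a second look while the link sheets still exist.

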5. TDF
6. TX energy KV: 50, 70, 100
7. Total dose
8. Break duration (days or N/A)

E. Outcomes:

1. Cured: Yes/No
2. Adverse Events: yes, no
3. Adverse Events description (as applicable)
4. Notes (as applicable)

**F. Follow-Up:**

1. Time in months since the most recent follow-up since end of treatment
2. Recurrence: Yes/No
3. Recurrence treatment and outcome (as applicable)
4. Follow-up notes (as applicable)

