## **5.3. STUDY DURATION, ENROLLMENT AND NUMBER OF SITES**

### **5.3.1. Duration of Study**

Applicable data elements to be reviewed in this study will be collected from patient records whose treatment of NMSC with the SRT-100™ occurred prior to 01/01/2015. All applicable and available data elements as specified in this study protocol will be recorded for each patient from the time of treatment forward to the most recent follow-up data entry date.

Therefore, the study duration of patient participation in this study according to the duration of the review of their medical records will vary individually based upon their initial SRT-100™ treatment date.

The entire study duration with respect to time from start of patient data identification and collation to completion of the final patient data entry will be dependent upon the time needed to identify all potential participating study sites and to collate all of the required available data from all qualifying patient records at each of those sites.

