## **10. RESULTS ANALYSIS**

### **10.1. PRIMARY ANALYSIS**

Primary analysis of the retrospective data set will be assessment of cure rates and incidence of reoccurrence of lesions.

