#### **10.1.2. Recurrences and Complications**

Each identified incidence of lesion recurrence, complication or adverse event recorded at any point throughout the treatment and follow-up evaluation phase will be explored descriptively. Statistical evaluation of recurrences will be as follows:

- (i) *Kaplan-Meier Survival Probability Estimates* will be calculated across the duration of available follow-up data, reporting survival probability estimates, and lower and upper limits of the 95% Confidence Interval by follow-up year.
- (ii) *Log-Rank Test* will be performed to evaluate for differences in recurrence-free survival between lesion types.
- (iii) *Multivariate Cox Regression Analysis* will be performed to account for the contribution of the potential influential factors of gender, age, lesion type, lesion size, total treatment dosage and TDF to recurrence-free survival.

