### **10.2.3. Treatment and Follow-Up**

- (i) *Treatment Period*: Descriptive evaluation (mean, standard deviation and range) of the number of treatment days will be calculated for lesions overall and by lesion type. T-test analysis for two independent samples will be applied to assess for any difference in the number of treatment days (the treatment administration period) between lesion types. A two-tailed p value of <0.05 will be considered statistically significant and indicative of a clinically meaningful difference.
- (ii) *Follow-Up Evaluation Period*: Descriptive evaluation (mean, standard deviation and range) of the number of follow-up months will be calculated for lesions overall and by lesion type. T-test analysis for two independent samples will be applied to assess for any difference in the number of follow-up months (the follow-up evaluation period) between lesion types. A two-tailed p value of <0.05 will be considered statistically significant and indicative of a clinically meaningful difference. The categorical distribution (number and percentage) of the follow-up evaluation period by year for all lesions and by lesion type will also be calculated.

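### No time of recurrence is collected, although the Kaplan-Meier, log-rank and Cox analyses need one; where follow-up runs past a recurrence, early recurrence is understated

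*Combined protocol and SAP*

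**What the plan says.** Section 6.3 F lists four follow-up elements: "Time in months since the most recent follow-up since end of treatment"; recurrence as yes or no; treatment and outcome of any recurrence; and free-text notes where applicable. Parts A to E of Section 6.3 contain no date or time of recurrence.

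Section 5.3.1 says that data "will be recorded for each patient from the time of treatment forward to the most recent follow-up data entry date". It sets no stop at recurrence. Section 7 says that "the study site staff member will extract only the required data elements and enter them directly into an Excel database". Under Section 7.2.1, the sheet linking code to chart is destroyed once the data have been entered and checked.

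Section 10.1 makes recurrence part of the main result: "Primary analysis of the retrospective data set will be assessment of cure rates and incidence of reoccurrence of lesions". Section 10.1.2 then plans three time-to-event analyses: Kaplan-Meier, "reporting survival probability estimates, and lower and upper limits of the 95% Confidence Interval by follow-up year"; a log-rank test, which "will be performed to evaluate for differences in recurrence-free survival between lesion types"; and a multivariate Cox regression. It defines no time origin, event time or censoring time.

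**The concern.** All three analyses need the time at which each recurrence was found. The database will hold only the time of the last visit. The two coincide when the recurrence visit is the last chart entry, and then there is no error. They differ when the patient was seen again, and the plan expects that for some lesions because it asks for the treatment and outcome of the recurrence.

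Late dating can only move events to the right, so the early-year recurrence estimates come out too low, in the device's favour. Later in the curve the same events fall on a smaller risk set, so the error can go either way. The comparison of lesion types is also exposed. If BCC and SCC lesions were followed for different lengths of time, the misdated events reflect follow-up as well as recurrence. Section 10.2.3 plans to test for that very difference: "T-test analysis for two independent samples will be applied to assess for any difference in the number of follow-up months".

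**Working it through.** The plan gives no sample size, event count or power for these analyses, so there is no figure of its own to reproduce. The check asks what the analyses return when recurrences are dated late.

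**Inputs**
- True recurrence: 1.9% at 2 years and 5.0% at 5 years (abstract in Section 3).
- Hazard in years 0-2: −ln(0.981)/2 = 0.00959 per year. After year 2: [−ln(0.95) + ln(0.981)]/3 = 0.01070 per year.
- True 1-year recurrence: 1 − exp(−0.00959) = 0.95%.
- Follow-up (assumed): uniform 0-8, 0-6 or 1-7 years, or exponential with mean 3 or 4 years.
- Dating (assumed): recurrence plus 6 or 12 months, or end of follow-up if sooner; or half or all of the recurrences dated at an independent last follow-up.

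**Kaplan-Meier, 1.5 million simulated lesions per scenario; ranges are across the five follow-up distributions**

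| Dating of recurrences | 2 years (true 1.9%) | 5 years (true 5.0%) |
|---|---|---|
| Recurrence visit is last entry | no bias | no bias |
| 6 months late | 1.5-1.7% | 5.0-5.3% |
| 12 months late | 1.1-1.4% | 4.9-5.6% |
| Half at last follow-up | 1.1-1.3% | 3.9-5.3% |
| All at last follow-up | 0.3-0.6% | 2.8-5.5% |

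At 1 year (true 0.95%) the estimate is 0.5-0.6% with a 6-month lag and 0-0.2% with a 12-month lag. The 0% arises by construction, because follow-up uniform on 1-7 years allows no exit before year 1. The 5-year upper ends vary by about 0.1 point between runs.

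**Hand check of the worst case.** If every recurrence is dated at last follow-up, a recurred lesion stays in the risk set until follow-up ends. The apparent hazard at time t is then (rate at which follow-up ends at t) × (probability of recurrence by t), the second factor being about 0.00959t up to year 2. Integrated from 0 to 2 years:
- Uniform 0-8: 0.00959 × [8 ln(8/6) − 2] = 0.00959 × 0.3015 = 0.29%.
- Uniform 0-6: 0.00959 × [6 ln(6/4) − 2] = 0.00959 × 0.4328 = 0.42%.
- Exponential, mean 3: (1/3) × 0.00959 × 2 = 0.64%.
- Exponential, mean 4: (1/4) × 0.00959 × 2 = 0.48%.

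These agree with the simulated 0.29, 0.42, 0.64 and 0.48%.

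**Log-rank and Cox.** The log-rank figures use 1,715 lesions (the size of the Section 3 study) in two equal groups, 2,000 replicates and a two-sided 5% level. With equal follow-up the test rejects about 5% under no true difference, and a true hazard ratio of 2.0 reads 1.96-2.03. With unequal follow-up and no true difference (hazard ratio of the shorter-followed group):

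| Dating | Uniform 0-8 v 0-6 y: rejects / HR | Exponential mean 4 v 3 y: rejects / HR |
|---|---|---|
| 6 months late | 6% / 1.09 | 6% / 1.04 |
| 12 months late | 11% / 1.20 | 6% / 1.07 |
| Half at last follow-up | 32% / 1.52 | 8% / 1.15 |
| All at last follow-up | 87% / 2.72 | 18% / 1.32 |

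The last exponential entry also follows by hand. With all events misdated and equal true recurrence, the hazard ratio reduces to the ratio of the rates at which follow-up ends, (1/3)/(1/4) = 1.33.

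**The case against.** Nothing in the documents closes the gap, but several points limit it.

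- **Frequency is unknown.** The documents do not say how many recurrences are followed by later visits. The text supports some lesions being misdated; it does not support a share. This stands.
- **Dates may be recoverable.** Recurrence treatment and follow-up notes are listed elements, Section 10.1.2 has each recurrence explored descriptively, and the link sheet survives until the data are checked. That gives a window for repair, but no date is required, so a database without one would pass a completeness check.
- **The first item of 6.3 F is garbled.** Months from end of treatment to last follow-up is the likeliest reading. No natural reading makes it the time of recurrence.
- **Moderate shifts are within sampling error.** The 6-month, 12-month and half-misdated results all lie inside the Section 3 study's intervals (1%-2.7% at 2 years, 3.2%-6.7% at 5 years). At 2 years they amount to 1.9 − 1.7 = 0.2 to 1.9 − 1.1 = 0.8 points. This is true, but the early-year bias has a known direction and does not shrink as lesions are added.
- **The large log-rank errors need stacked assumptions.** The 32% and 87% require unequal follow-up with a hard upper limit and half or all events at an independent last visit. With exponential follow-up the first three dating rules give only 6-8%. These figures are illustrations, not expected error.
- **The cure rate is untouched.** Section 2 names long-term cure rate as the primary outcome, and the percentage in 10.1.1 does not use event times. But Section 10.1 puts recurrence incidence in the primary analysis as well.

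**Conclusion.** The concern holds and needs correction before data collection closes. A component of the primary analysis lacks an input that it cannot do without, and the loss becomes permanent when the link sheets are destroyed.

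The direction is certain for the early years: recurrence is understated wherever follow-up continues past the event. The size is not known. It depends on the assumed recurrence rates, the assumed follow-up distributions and the share of recurrences with later visits. A lag of 6 to 12 months would remove roughly a tenth to two-fifths of the 2-year recurrence (0.2/1.9 = 11% to 0.8/1.9 = 42%). The all-misdated case is an outer bound. The log-rank and Cox results are little affected if BCC and SCC follow-up is similar, and can show a false difference if it is not.

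**What to change.** - In Section 6.3 F, add a required element for every lesion with Recurrence = Yes: months from end of treatment to first documented recurrence.
- In Section 10.1.2, state that recurrence-free time runs from end of treatment to first documented recurrence, and is censored at last follow-up if there is none.
- As an editorial correction, reword the first item of 6.3 F as months from end of treatment to most recent follow-up.

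While 10.1.2 is open, it should also say how lesions recorded as not cured enter recurrence-free survival. One option is to exclude them as never at risk of recurrence, with a sensitivity analysis counting them as failures at time zero. This is a separate missing detail, and the verdict does not rest on it.

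The cost is one column in the Excel database and two sentences in 10.1.2. Charts of recurred lesions already abstracted must be re-opened before the link sheets are destroyed. If recurrence is as in the Section 3 study, that is about 5% of lesions or fewer; in a registry of that study's size, 0.05 × 1,715 ≈ 86 lesions.

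### The only follow-up time field literally asks for months since the last visit, not months of follow-up, and neither the end of follow-up nor the time of recurrence is defined

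*Combined protocol and SAP*

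**What the plan says.** Section 6.3 F lists one follow-up time, "Time in months since the most recent follow-up since end of treatment", then "Recurrence: Yes/No", then recurrence treatment and outcome, and notes. Sections 6.3 A to F list no treatment date, visit date or recurrence date.

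Other sections describe a different quantity. Section 5.3.1 has data recorded "from the time of treatment forward to the most recent follow-up data entry date". Section 10.2.3(ii) summarises "the number of follow-up months (the follow-up evaluation period" and tabulates it by year. In 10.1.2(i) the Kaplan-Meier estimates "will be calculated across the duration of available follow-up data, reporting survival probability estimates" by follow-up year, and the log-rank test and Cox model there use the same time.

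No minimum follow-up is set. Inclusion criterion 7 asks only that "Required retrospective data is existing and sufficient". Under 7.2.1, the sheets linking codes to charts are destroyed once the data have been entered and double-checked.

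**The concern.** F(1) contains the word *since* twice. As grammar, it is the gap between the last post-treatment visit and the day the chart is reviewed. For lesions treated and abstracted on the same dates, that gap runs exactly opposite to length of follow-up: the lesion lost soonest gets the largest number.

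This one number is the time axis for every time-to-event analysis in 10.1.2, and long-term outcome is the purpose of the study. Staff at an unlimited number of sites enter it directly. If sites read it differently, two scales are mixed in one column and no other required field shows which is which.

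Two gaps remain even when the field is read as intended:

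- Follow-up ends at the latest follow-up entry, whether or not the treated site was examined, so unobserved time can count as recurrence-free.
- Recurrence is Yes/No with no time attached, so a recurred lesion can only carry its last-visit time.

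**Working it through.** The plan gives no sample size, event count or target precision, so it has no figure of its own to reproduce.

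**Inputs from the documents.** Treatment "whose treatment of NMSC with the SRT-100™ occurred prior to 01/01/2015" (5.3.1; inclusion criterion 3 instead allows dates to the end of 2015, which does not change the argument). The reference list includes a February 2018 item, so abstraction under this version is taken to start no earlier than that. The 2012 retrospective study in section 3 reports cumulative recurrence of 1.9% at 2 years and 5.0% at 5 years.

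**Step 1: what the literal field returns.** Literal value = (end of treatment to abstraction) − (end of treatment to last follow-up).

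- Treated at end of December 2014, last seen one month later, abstracted February 2018: 1 month observed, about 36 entered.
- Treated January 2013, last seen January 2014, abstracted February 2018: 12 observed, 61 − 12 = 49 entered.
- Treated January 2013, last seen January 2018, abstracted February 2018: 60 observed, 61 − 60 = 1 entered.
- Treated at the start of 2013, abstracted mid-2018 (66 months later): last seen at 3, 12 or 36 months gives 63, 54 or 30.
- The same lesions abstracted at the start of 2021 (96 months later): 93, 84 or 60.

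The third example matters as much as the first two, because well-followed lesions leave the late risk sets.

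**Step 2: effect on the curves.** I simulated 400,000 lesions per scenario with a constant recurrence hazard of −ln(0.95)/60 = 0.000855 per month. This gives 5.0% at 5 years and 1 − 0.95^(24/60) = 2.03% at 2 years, close to the cited 1.9%. Assumptions not in the documents: treatment dates uniform over 2010 to 2014, abstraction in mid-2018 or at the start of 2021, exponential loss to follow-up with median 12, 24 or 48 months, and every record literal.

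| Abstraction, median loss | Correct time: 2 y / 5 y | Literal F(1): 2 y / 5 y | End of treatment to last visit, no recurrence time: 2 y / 5 y | Shown at risk at 5 y: correct → literal |
|---|---|---|---|---|
| mid-2018, 12 mo | 2.10% / 4.94% | 0.41% / 1.46% | 1.47% / 9.80% | 2.2% → 44.5% |
| mid-2018, 24 mo | 2.01% / 4.99% | 1.50% / 3.20% | 0.71% / 5.72% | 12.1% → 30.0% |
| mid-2018, 48 mo | 2.05% / 5.03% | 3.25% / 5.44% | 0.36% / 3.75% | 28.5% → 17.8% |
| 2021, 12 mo | 2.05% / 4.85% | 0.11% / 0.56% | 1.45% / 8.30% | 3.1% → 86.4% |
| 2021, 24 mo | 2.02% / 4.98% | 0.90% / 2.01% | 0.72% / 4.23% | 17.0% → 66.9% |
| 2021, 48 mo | 2.06% / 5.00% | 2.79% / 4.58% | 0.36% / 2.23% | 40.2% → 44.3% |

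The literal value correlated −0.66 to −0.89 with true follow-up. The literal 5-year estimate was too low in five of the six scenarios. With median loss at 48 months, the literal 2-year estimate was too high in both.

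**Step 3: rewording alone is not enough.** The fourth column uses the intended interval but gives each recurred lesion its last-visit time. It assumes that visits continue after recurrence as they would have otherwise. Two-year recurrence is always understated, and the 5-year figure ranges from 2.23% to 9.80%. Where follow-up stops at the recurrence visit, this error disappears. Only the correct time (recurrence if it occurred, otherwise last follow-up) recovers the input in every scenario.

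**Step 4: the loose end of follow-up.** Its size depends on how often the latest follow-up entry falls after the last examination of the treated site. The documents give no figure, so I put no number on it. Its direction is toward understated recurrence.

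**The case against.** The strongest reply is that the meaning is plain in context. F(1) sits under a follow-up heading and mentions end of treatment. Sections 5.3.1 and 10.2.3(ii) describe an interval running forward from treatment, and the literal reading needs a chart-review date that the plan neither names nor collects. Site staff are trained to the protocol. This largely stands: it is mainly a drafting error, and harm from it needs some sites to follow the words. But the training text contains those words, and no section redefines the field.

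A reader might infer three stronger claims that the documents do not support:

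- **That any chart entry extends follow-up.** Section 5.3.1 refers to follow-up data, and 6.2 to post-procedure follow-up data. A telephone call, or a visit about another lesion, is neither admitted nor ruled out. The supportable gap is that examination of the treated site is not required.
- **That a misreading can never be caught.** Until the link sheets are destroyed, 7.2.1 leaves room to check against the chart. Such a check may simply confirm a misread value while the definition stays ambiguous. Afterwards, the database alone cannot show it.
- **That the literal reading always lowers recurrence.** It also moves well-followed lesions to short times, and the table has estimates above the truth.

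The simulated sizes can fairly be challenged too. They rest on assumed dates and loss rates and on every record being misread.

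**Conclusion.** The point holds as a definitional fault in the time axis of the recurrence analyses. The field as worded and the analysis sections describe different quantities. The intended one can be inferred but is not stated where data are abstracted. Any site entering the literal value distorts the recurrence curves, often but not always downward. At worst in the simulated scenarios, about 4.9% at 5 years becomes 0.6%. A mix of sites was not simulated, and the share that would misread the field is unknown.

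The two remaining gaps need no misreading. Nothing ties the end of follow-up to an examination of the treated site, and no time of recurrence is recorded. The change should be made before abstraction, or at the latest before the link sheets are destroyed.

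**What to change.** 1. Replace F(1) with: *Months from last SRT-100 treatment to the most recent visit at which the treated site was examined and its status recorded.*
2. Add to F(2): *If yes, months from last SRT-100 treatment to first documented recurrence.*
3. In 10.1.2, state that recurred lesions enter at time to recurrence and all others are censored at the last examination of the treated site. Use matching wording in 5.3.1 and 10.2.3(ii).
4. Calculate both month values from dates kept only at the site, so that the central database still holds months and no dates. Include the two values in the 7.2.1 double-check, while the link to the chart still exists.

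The cost is slightly more abstraction work per lesion. For some lesions follow-up will be shorter, so late-year estimates will be less precise.
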